8.2.3 Pharmacodynamic Assessments

8.2.3.1 Plasma 5-HIAA

Fasting blood samples (≥ 6 hours) for measurement of 5-HIAA in plasma will be collected and analyzed by a specialty laboratory. All sample processing information will be supplied by the laboratory in a separate document/study manual. Efforts should be made to schedule these visits in the morning, with instructions to the patient to arrive in a fasted state and not dose prior to the blood draw.

8.2.4 Safety Assessments

In addition to the clinical laboratory assessments described in [Section 8.2.2](#), monitoring of AEs is also considered a safety assessment and is described in detail in [Section 9](#). Clinically significant changes compared with Baseline findings for these variables should be reported as AEs on the CRF. Clinically significant changes compared with Baseline values, which are determined to be AEs, should be followed until the event has resolved, the condition has stabilized, etiology of the event is determined to be not related to study drug, or the patient is lost to Follow-up.

8.2.4.1 Vital Sign Measurements

Measurement of vital signs will include assessment of blood pressure, respiratory rate, pulse rate, and oral temperature. Vital sign measurements should not be conducted with the 30 minutes immediately following any phlebotomy.

Efforts should be made to standardize blood pressure collection across all patients and visits. Patients should be seated for at least 5 minutes prior to collection. All measurements should be assessed on the same arm, and by the same technician where possible.

Additional measurements may be obtained if clinically indicated. Vital sign measurements will be measured as indicated in [Appendix A](#).

8.2.4.2 Physical Examinations

Complete physical examinations will be performed as outlined in [Appendix A](#). Complete physical examinations will include a minimum of a review of the patient's general appearance, head, eyes, ears, nose, and throat (HEENT), neck, heart, lungs, abdomen, back and extremities, skin, and general neurological system.

Symptom-oriented physical examinations will be performed at all other time points and as clinically indicated.

In addition, weight will be captured during each physical examination. Efforts should be made to standardize weight collection across all patients and visits. Patients should be instructed to remove shoes and heavy clothing (eg, heavy coats, jackets) prior to measurement. For weight collection, an effort should be made to use the same scale throughout the study where possible. In instances where multiple scales may be used, efforts should be made to reset the scale to zero prior to collection of weight measurement.

8.2.4.3 Electrocardiograms

Electrocardiograms (12-lead ECGs) will be performed as specified in [Appendix A](#).

8.2.4.4 Adverse Events of Special Interest

Monitoring of these events will be the responsibility of the DSMB. The process of data collection and assessment of the events will be detailed in a separate DSMB charter.

Additional information will be collected if episodes of any of the following AEs of special interest occur.

8.2.4.4.1 Central Nervous System Events

Central nervous system events of special interest may include any clinically significant changes in mood, physical affect, or exacerbation of preexisting CNS conditions (eg, depression, migraine headaches).

8.2.4.4.1.1 Depression Detection

Patients will be evaluated beginning at Day 1 (Baseline) and at each subsequent visit for indications of depression. During each visit the patient will first be asked to respond to the question “During the past month, have you often been bothered by feeling down, depressed, or hopeless?” Followed by “During the past month, have you often been bothered by little interest or pleasure in doing things?” A positive response prior to Day 1 dosing will be evaluated by the Investigator in order to assess if the response is clinically significant. Positive responses assessed as clinically significant prior to Day 1 dosing will be captured on the medical history CRF page. Positive responses following the first dose will be evaluated by the Investigator in order to assess if an AE has occurred. Positive responses assessed to be an AE will be followed as an AE of special interest.

8.3 Other Assessments

8.3.1 Chromogranin A (CgA)

Blood samples for measurement of chromogranin A (CgA) levels will be collected as indicated in [Appendix A](#).

8.3.2 Disease Progression

Data will also be collected on measures of disease progression as performed as standard of care including, but not limited to interpretation of clinical scans (eg, PET, CAT, MRI scans of tumor), or Investigator assessment of disease status, while the patient is enrolled in the study.

8.3.3 Quality of Sleep Assessment

Quality of sleep will also be evaluated beginning Day 1 (Baseline) and at each subsequent visit thereafter. Patients will be asked to respond to the following question “Since your last visit, how many times a night (on average) do you wake up due to your CS symptoms?” based on the following scale 0, 1, 2, 3, 4, >4.

8.4 Appropriateness of Assessments

The assessments used in this study conform to the usual clinical and laboratory assessments of patients with CS participating in clinical trials and are typical of a Phase 3 study.

9.1 Adverse Events

It is the responsibility of the Investigator to document all AEs that occur during the study.

Adverse event is defined as any untoward medical occurrence associated with the use of a drug in humans, whether or not considered drug related.

Life-threatening adverse event or life-threatening suspected adverse reaction: An adverse event or suspected adverse reaction is considered "life-threatening" if, in the view of either the Investigator or Sponsor, its occurrence places the patient or subject at immediate risk of death. It does not include an adverse event or suspected adverse reaction that, had it occurred in a more severe form, might have caused death.

An AE includes any noxious, pathological, or unintended change in anatomical, physiological, or metabolic functions as indicated by physical signs or symptoms occurring in any phase of the clinical study whether or not considered related to the study medication. This definition includes an exacerbation of preexisting medical conditions or events, historical condition not present prior to study treatment, which reappear following study treatment, intercurrent illnesses, hypersensitivity reactions, drug interaction, or the significant worsening of the disease under investigation that is not recorded elsewhere in the CRF. Anticipated day-to-day fluctuations of pre-existing conditions that do not represent a clinically significant exacerbation or worsening need not be considered AEs.

Any laboratory abnormality fulfilling the criteria for a SAE ([Section 9.2](#)) should be reported as such, in addition to being recorded as an AE. Any treatment-emergent abnormal laboratory result which is clinically significant, ie, meeting 1 or more of the following conditions, should be recorded as a single diagnosis AE:

- Is considered to be an SAE,
- Results in discontinuation from study treatment, or
- Results in a requirement for a change in concomitant therapy (ie, addition of concomitant therapy)

In the event of medically significant unexplained abnormal laboratory test values, the tests should be repeated and followed up until they have returned to the normal range and/or an adequate explanation of the abnormality is determined.

TEAEs are defined as any AEs reported after the first dose of study drug on Day 1. Adverse events reported after consent of a patient, but before administration of study medication, will be reported in the Medical History.

AEs should not be solicited with leading questions that suggest specific signs or symptoms. Rather, AEs should be solicited by asking the patient a non-leading question such as: “Do you feel different in any way since receiving the dose or since the last assessment?”

The Investigator will evaluate all AEs with regard to the maximum intensity and relationship to study drug, as follows:

- Maximum intensity

Maximum intensity should be assigned using 1 of the following 3 severity grades:

- Mild: aware of event but easily tolerated
- Moderate: discomfort, enough to cause interference with usual activity
- Severe: incapacitating; patient unable to work or perform usual activities

- Relationship to study drug

Not related:

- Does not follow a reasonable temporal sequence from administration of the drug
- Event is reasonably explained by other factors, including underlying disease, complications, concomitant drugs, or concurrent treatment; there is no reasonable causal link that drug caused the event.

Unlikely related:

- Temporal sequence from administration of the study drug to event onset suggests a doubtful or improbable causal relationship
- Alternative explanation (including underlying disease, complications, concomitant drugs, or concurrent treatment) is plausible and more likely

Possibly related:

- That follows a reasonable temporal sequence from administration of the drug (including the course after withdrawal of the drug), or
- For which the possibility of the study drug being the causative factor (eg, existence of similar reports attributed to the suspected drug and its analogues; reactions attributable to the pharmacological effect) could not be excluded, although other factors such as underlying disease, complications, concomitant drugs, or concurrent treatment are presumable.

Probably related:

- That follows a reasonable temporal sequence from administration of the drug (including the course after withdrawal of the drug), and
- For which the possibility of factors other than the drug, such as underlying disease, complications, concomitant drugs, or concurrent treatment, could not be excluded as the cause.

Definitely related:

- Follows a clear temporal sequence from administration of the study drug.
- Could not be possibly explained by the known characteristics of the patient's clinical state, environmental or toxic factors, or other modes of therapy administered to the patient.
- Disappears or decreases on cessation or reduction in dose of the study drug.
- Reappears or worsens when the study drug is re-administered.
- Follows a response pattern known to be associated with administration of the study drug.

The degree of certainty with which an AE is attributed to treatment with study medication (or alternative causes, eg, natural history of the underlying diseases, concomitant therapy, etc.) will be determined by how well the event can be understood in terms of known pharmacology of the study medication and/or reaction of similar nature being previously observed with the study medication or the class of study medication.

All AEs should be followed for at least 30 days following the last dose of study drug or until the event has resolved, the condition has stabilized, or the patient is lost to Follow-up. For each patient for whom an AE was reported that did not resolve before the end of the reporting period, Follow-up information on the subsequent course of events must be submitted to the Sponsor. This requirement indicates that follow-up may be required for some AEs after the patient has completed his/her participation in the study

9.2 Serious Adverse Events (SAEs)

An SAE is defined as any event that results in any of the following outcomes:

1. Death
2. A life-threatening adverse event;
3. Inpatient hospitalization or prolonging of an existing hospitalization (see [Section 9.2.1](#) for information on hospitalization as an SAE);

4. A persistent or significant incapacity or substantial disruption of the ability to conduct normal life functions; or
5. A congenital anomaly/birth defect.

Important medical events that may not result in death, be life-threatening, or require hospitalization may be considered serious when, based upon appropriate medical judgment, they may jeopardize the subject and may require medical or surgical intervention to prevent one of the outcomes listed above.

Any SAE must be reported by telephone or facsimile within 24 hours of discovery of the event. Investigators should not wait to receive additional information to fully document the event before notifying the Sponsor of an SAE at:

Sites in North America must report to:

Safety Data [contact]

Email address (in case of fax failure): [contact]

Sites outside North America must report to the country specific toll-free fax numbers identified below:

Australia: [REDACTED]
Belgium: [REDACTED]
Brazil: [REDACTED]
France: [REDACTED]
Germany: [REDACTED]
Israel: [REDACTED]
Italy: [REDACTED]
Netherlands: [REDACTED]
Spain: [REDACTED]
Sweden: [REDACTED]
United Kingdom: [REDACTED]

Email Address (in case of fax failure): [REDACTED]

The telephone report should be followed by full written summary detailing relevant aspects of the SAE in question using the provided SAE report form. Where applicable, information from relevant hospital case records and autopsy reports should be obtained. The SAE should also be recorded on the AE page of the patient's CRF.

An SAE that occurs after completion of the study but, in the opinion of the Investigator, is related to the study medication, should be reported as described for an SAE. If an AE does not meet the regulatory definition of "serious" but is considered by the Investigator to be

related to the study medication and of such clinical concern as to influence the overall assessment of safety, it must be reported as defined for an SAE.

All patients (including discontinued patients) with a SAE must be followed until the event resolves or reaches a new Baseline, but for a minimum of 30 days after the last dose of study drug.

9.2.1 Hospitalization as an SAE

Hospitalization is defined as any in-patient overnight stay in a hospital. A hospitalization in and of itself does not constitute an SAE. The condition which caused the hospitalization must be evaluated and determined to be an AE. Although an AE which results in hospitalization is an SAE, patients are hospitalized for a variety of reasons which may not be associated with or considered an SAE (eg, convenience, logistics, preference, etc). Therefore, each case of hospitalization must be evaluated separately.

For example, the following would not be considered SAEs:

- Hospitalization for a preexisting condition which did not worsen (eg, cataract surgery)
- Hospitalization solely for a procedure or treatment that was not performed to treat an AE
- Hospitalization for a condition that does not normally require treatment, but electively done (eg, cosmetic surgery)
- Hospitalization strictly for convenience reasons or observations (eg, procedures only performed in a hospital because of the distance the subject lives from the hospital)

9.3 Suspected Unexpected Serious Adverse Reactions (SUSARs)

The FDA and/or other applicable Regulatory Authorities and all participating Investigators will be notified by a written Investigational New Drug Application (IND) safety report and/or other applicable regulatory report (eg, SUSAR) of any suspected adverse reaction that is both serious and unexpected, no later than 15 calendar days from the “date learned” of the event. In addition, all applicable regulatory bodies will be notified within 7 calendar days of any unexpected fatal or life-threatening suspected adverse reaction.

An adverse reaction is defined as any untoward and unintended response to an investigational medicinal product (IMP) related to any dose administered. This definition also covers medication errors and uses outside what is foreseen in the protocol, including misuse and abuse of the product. The definition also implies a reasonable possibility of a causal relationship between the event and the IMP.

An unexpected adverse reaction is any adverse drug event, which is not listed in the current Investigator's Brochure or is not listed at the specificity or severity that has been observed. For example, (A) a single occurrence of an event that is uncommon and known to be strongly associated with drug exposure (eg, angioedema, hepatic injury, Stevens-Johnson Syndrome); (B) 1 or more occurrences of an event that is not commonly associated with drug exposure, but is otherwise uncommon in the population exposed to the drug (eg, tendon rupture); (C) an aggregate analysis of specific events observed in a clinical trial (such as known consequences of the underlying disease or condition under investigation or other events that commonly occur in the study population independent of drug therapy) that indicates those events occur more frequently in the drug treatment group than in a concurrent or historical control group.

An untoward and unintended response to a non-IMP is by definition not a SUSAR.

9.4 Precautions

9.4.1 Pregnancy

Any patient (or patient's partner) who becomes pregnant during the study should be followed through delivery or termination of the pregnancy. In addition, patients who become pregnant during the study must be discontinued from the study treatment immediately.

In pregnancies that progress to term, any congenital abnormalities/birth defects in the offspring of a patient who received study medication should be reported as an SAE. The outcome of the pregnancy and the presence or absence of a congenital abnormality will be documented by completion of a Pregnancy Questionnaire and a Pregnancy Outcome Form in accordance with GCP and ICH guidelines and the Sponsor's SOPs.

Female patients should also notify the Investigator if they become pregnant within 30 days after last dose of study medication. Male patients should notify the Investigator if a female partner becomes pregnant within 30 days after last dose of study medication. The Sponsor must be notified of all pregnancies reported to the Investigator (see [Section 9.2](#) for contact information).

10. Statistical Methodology

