6.1 Inclusion Criteria

Patients must meet all of the following criteria to be considered eligible to participate in the study:

1. Ongoing participation in a Phase 2 study (ie, LX1606.1-202-CS, LX1606.1-203-CS) or Phase 3 study (ie, LX1606.1-301-CS, LX1606.1-303-CS)
2. Patients of childbearing potential must agree to use an adequate method of contraception (defined as having a failure rate of <1% per year) during the study and for 12 weeks after the Follow-up visit. Adequate methods of contraception for patients or partner include condoms with spermicide gel, diaphragm with spermicide gel, coil (intrauterine device), surgical sterilization, vasectomy, oral contraceptive pill, depot progesterone injections, progesterone implant, and abstinence during the study and for 12 weeks after the Follow-up Visit.
 - a. Childbearing potential is defined as those who have not undergone surgical sterilization, or those who are not considered postmenopausal. Postmenopause is defined as absence of menstruation for at least 2 years. If necessary, follicle-stimulating hormone (FSH) results >50 IU/L at Baseline Day 1 are confirmatory in the absence of a clear postmenopausal history.
3. Ability and willingness to provide written informed consent prior to participation in any study-related procedure.

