11.4.5 Retention of Study Documents

According to 21 CFR Part 312.62 and ICH E6, study-related records must be retained for at least 2 years after the last approval of a marketing application in an ICH region and until there are no pending or contemplated marketing applications in an ICH region, or at least 2 years have elapsed since the formal discontinuation of clinical development of the investigational product. These documents should be retained for a longer period, however, if required by applicable regulatory requirements or by an agreement with the Sponsor.

The Investigator must not destroy any study-related records without receiving approval from the Sponsor. The Investigator must notify the Sponsor in the event of accidental loss or destruction of any study records. If the Investigator leaves the institution where the study was conducted, the Sponsor must be contacted to arrange alternative record storage options.

12. Administrative Structure of the Study

The study will be monitored by Sponsor personnel or Sponsor representative. The following functions for this study will be performed by organizations designated by the Sponsor: data management and statistical analysis, including PD analysis and reporting.

13. Appendix A – Schedule of Events

Procedure	Treatment Period ⁶															EOS ⁴	2-Week Follow-up
	Baseline Day 1 ¹	Week 12	Week 24	Week 36	Week 48	Week 60	Week 72	Week 84	Week 96	Week 108	Week 120	Week 132	Week 144	Week 156	Week 168		
Tolerance (days)	NA	± 5	± 5	± 5	± 5	± 5	± 5	± 5	± 5	± 5	± 5	± 5	± 5	± 5	± 5	+ 21	± 5
Inclusion/Exclusion criteria	X																
Medical history	X																
Physical examination incl. weight	X	X ³	X ³	X ³	X	X ³	X ³	X	X ³	X ³	X ³	X	X ³	X ³	X ³	X	X ⁵
Urine pregnancy test ²	X	X	X	X	X	X	X	X	X	X	X	X	X	X	X	X	X
Hematology, Blood chemistry	X	X	X	X	X	X	X	X	X	X	X	X	X	X	X	X	X ⁵
Urinalysis	X				X			X				X				X	X ⁵
Chromogranin A	X				X			X				X				X	
Vital signs	X	X	X	X	X	X	X	X	X	X	X	X	X	X	X	X	X
ECG	X				X			X				X				X	X ⁵
Subjective Global Assessment	X	X	X	X	X	X	X	X									
EORTC QLQ-C30 & GI.NET21	X		X		X		X	X									
Sleep and Depression Assessment	X	X	X	X	X	X	X	X	X	X	X	X	X	X	X	X	X
Plasma 5-HIAA	X	X	X	X	X	X	X	X	X	X	X	X	X	X	X	X	X
Dispensation of LX1606	X	X	X	X	X	X	X	X	X	X	X	X	X	X	X	X	
Concomitant medications	X	X	X	X	X	X	X	X	X	X	X	X	X	X	X	X	X
Adverse events	X	X	X	X	X	X	X	X	X	X	X	X	X	X	X	X	X

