¹Eligibility will be determined at last visit of the original protocol; Day 1 will replace the next scheduled visit in the original protocol schedule. Visits should coincide with LAR injections for those patients receiving SSA therapy.
²Females of child-bearing potential only. ³Brief physical examination only (symptom-oriented, including weight). ⁴Visit to be performed for subjects who withdraw early and will not return for a 2-week follow-up visit; in all other cases the End-of-Study (EOS) visit should be performed followed by the follow-up visit 2 weeks after the final dose. ⁵To be performed only if evaluation at EOS is abnormal. ⁶All patients will receive LX1606 for at least 52 weeks and may continue treatment in the trial until such time telotristat etiprate has received regulatory approval to be marketed and is available via prescription or until 31 March 2017, whichever occurs first. Patients who reach this timeline event will be deemed to have completed the Treatment Period and will advance to the EOS visit, regardless of where they are in the visit schedule and when their last study visit occurred. The EOS visit should be performed within 21 calendar days following the completion of the Treatment Period.

14. Appendix B – Amount of Blood to be Collected from Each Patient

Assessment		Sample volume (mL)	Number of samples*	Estimated total volume (mL)
Safety	Hematology	2	17	34
	Blood chemistry	6	17	102
Other	CgA	2	5	10
Pharmacodynamic	Plasma 5-HIAA	4	17	68
			Total	214
*Maximum number of samples is indicated				

16. Appendix D – EORTC QLQ - GI.NET21

ENGLISH

EORTC QLQ – GI.NET21

Patients sometimes report that they have the following symptoms or problems. Please indicate the extent to which you have experienced these symptoms or problems during the past week. Please answer by circling the number that best applies to you.

During the past week:		Not at all	A little	Quite a bit	Very much	
31.	Did you have hot flushes?	1	2	3	4	
32.	Have you noticed or been told by others that you looked flushed/red?	1	2	3	4	
33.	Did you have night sweats?	1	2	3	4	
34.	Did you have abdominal discomfort?	1	2	3	4	
35.	Did you have a bloated feeling in your abdomen?	1	2	3	4	
36.	Have you had a problem with passing wind/gas/flatulence?	1	2	3	4	
37.	Have you had acid indigestion or heartburn?	1	2	3	4	
38.	Have you had difficulties with eating?	1	2	3	4	
39.	Have you had side-effects from your treatment? (If you are not on treatment please circle N/A)	N/A	1	2	3	4

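### Pregnancy notification stops 30 days after the last dose, although the protocol requires contraception to about day 98

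*Protocol*

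**What the plan says.** **Contraception.** Section 6.1, criterion 2 (repeated in the Synopsis), requires patients of childbearing potential to use adequate contraception "during the study and for 12 weeks after the Follow-up visit".

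**Timing of the Follow-up visit.** Appendix A, footnote 4, reads "in all other cases the End-of-Study (EOS) visit should be performed followed by the follow-up visit 2 weeks after the final dose". The tolerance row allows ±5 days for this visit. It is the last visit in the schedule and the last one with an entry in the row "Urine pregnancy test".

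**Notification.** Section 9.4.1 says "Female patients should also notify the Investigator if they become pregnant within 30 days after last dose of study medication", and for partners "Male patients should notify the Investigator if a female partner becomes pregnant within 30 days after last dose of study medication".

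**Provisions around these.** The sentence on following a pregnancy to outcome covers any patient or partner "who becomes pregnant during the study should be followed through delivery or termination of the pregnancy". Three other provisions in Section 9.4.1 carry no time limit:
- the outcome documentation: "The outcome of the pregnancy and the presence or absence of a congenital abnormality will be documented by completion of a Pregnancy Questionnaire", together with an outcome form;
- the rule that birth defects in the offspring of a treated patient are SAEs;
- the Sponsor's right to be told of every pregnancy that reaches the Investigator.

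The contraception and notification rules stand in the current Amendment 4 text and also in Amendments 3 and 2.

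**The concern.** Section 6.1 fixes the period after treatment in which pregnancy is to be avoided. Section 9.4.1 fixes the period in which a pregnancy is to be reported, and that period is much shorter. From day 31 to the end of the contraception period, a patient is still asked to avoid pregnancy but is not asked to tell anyone if one occurs, and no test is scheduled that would reveal it. Whether the Sponsor learns of it then depends on the patient volunteering the information.

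Safety is the primary objective, and Section 9.2 lists congenital anomaly as an SAE criterion. What is at stake is complete capture of a rare safety outcome. No estimate or planned analysis depends on it.

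**Working it through.** The protocol states no figure for this interval, so there is nothing to reproduce. The check is day arithmetic, counting from the last dose.

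**Inputs**
- Follow-up visit: day 14, tolerance ±5, so day 9 to 19 (Appendix A).
- Contraception after that visit: 12 × 7 = 84 days (Section 6.1).
- Notification window: 30 days (Section 9.4.1).

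**Formulas**
- End of contraception = Follow-up day + 84.
- Days without a notification request = end of contraception − 30.

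| Follow-up visit | End of contraception | Days without request | Share of period |
|---|---|---|---|
| Day 9 | 9 + 84 = 93 | 93 − 30 = 63 | 63/93 = 68% |
| Day 14 | 14 + 84 = 98 | 98 − 30 = 68 | 68/98 = 69% |
| Day 19 | 19 + 84 = 103 | 103 − 30 = 73 | 73/103 = 71% |

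**After the last scheduled test.** From the test on day 14 to day 98 is 84 days. The notification request covers 30 − 14 = 16 of them and leaves 84 − 16 = 68.

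**Does the during-the-study wording close the gap?** No. With the Follow-up visit on day 9 to 19, participation ends before day 30, so that wording adds nothing after day 30.

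**Late End-of-Study visit.** Appendix A allows that visit up to 21 days after treatment ends. If the Follow-up visit were therefore no earlier than day 21 (an assumption), contraception would end on day 21 + 84 = 105 and the gap would be 105 − 30 = 75 days. A late visit widens the gap.

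**Follow-up visit missed.** Footnote 4 provides for early withdrawals who do not return for it, and Section 6.1 then gives no end date for contraception. Two assumed readings:
- 12 weeks from the last dose: 84 − 30 = 54 days (64%).
- 14 weeks from the last dose: 98 − 30 = 68 days (69%).

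A pregnancy that starts by day 30 but is recognised later is still inside the request, because the window refers to becoming pregnant and not to detection.

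**The case against.** The strongest case against is that nothing here is wrong. Contraception and notification serve different purposes, and a preventive period may carry a margin beyond the period in which events are solicited. To call 30 days too short, one would have to show that conception after day 30 is relevant to exposure, and the protocol gives no half-life or reproductive-toxicity figure for that. Thirty days is also the protocol's general safety convention: it applies to SAE reporting after discontinuation (Section 6.3), AE follow-up (9.1), minimum SAE follow-up (9.2) and on-study deaths (10.4.2.1). Birth defects are SAEs without a time limit, and Section 9.2 also asks for SAEs after study completion that are judged related. Consent pages, the Sponsor's SOPs and the text just before Section 9.1 are not visible and may tell patients to report later. Finally, an amendment needs IRB/ERC approval (Section 11.3), and the regional amendments would need the same edit in parallel.

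Much of this stands. There is no contradiction, no harm is measured, and the statement can only be made about the visible text. Two parts do not remove the point. The untimed routes work only once the site has learned of the pregnancy or birth, and what is missing is the request that would bring that about. The other 30-day windows concern AEs, SAEs and deaths, for which the protocol sets no longer precautionary period, whereas for pregnancy it does. The approval step is modest if the edit goes into an amendment made for other reasons.

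**Conclusion.** The point holds as a minor, inexpensive improvement. For patients who attend the Follow-up visit, the notification request leaves out 68 of the 98 days of post-treatment contraception as scheduled, or 63 of 93 to 73 of 103 with the visit tolerance. These are calendar days and not a measure of risk. Up to 130 patients are expected, and it is assumed that few are of childbearing potential.

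The conclusion is firm for female patients. For partners of male patients it depends on how criterion 2 is read. The criterion mentions methods for patients or partner, but its definition, "Childbearing potential is defined as those who have not undergone surgical sterilization, or those who are not considered postmenopausal", turns on sterilization and menopause and does not spell out how male patients are bound. No endpoint, estimate or planned analysis changes.

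**What to change.** In Section 9.4.1, replace the 30-day limit in both notification sentences (female patients, and partners of male patients) with: through the end of the contraception period in Section 6.1, that is, 12 weeks after the Follow-up visit, or 14 weeks after the last dose if that visit is missed. Add that pregnancies reported in this period are followed to outcome, since the present follow-to-outcome sentence is limited to pregnancies during the study. The 14-week limit also gives an end date for early withdrawals, for whom Section 6.1 now gives none.

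The cost is a few extra reports and outcome follow-ups, a possible change to the consent wording, and IRB/ERC approval, which can be sought with the next amendment in each region. Nothing changes in the analysis.
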